Q1. Yesterday, did you have a headache that lasted for thirty minutes or more?	Yes	Migraine if at least two migraine Criteria A's and at least one migraine Criteria B.
,	No ^a	
Q2. Enter the total number of hours you had a headache yesterday.	Range 1 to 24	If ≥1, the headache will be counted as a headache day.
Q3. Yesterday, what was the worst	Mild	
headache pain?	Moderate	Migraine Criteria A
	Severe	Migraine Criteria A
Q4. Yesterday, was the headache	Yes	Migraine Criteria A
throbbing or pounding?	No	
Q5. Yesterday, was the headache just on	Yes	Migraine Criteria A
the right or left side of your head?	No	
Q6. Yesterday, was the headache made	Yes	Migraine Criteria A
worse by your usual daily activity	No	
Q7. Yesterday, did the headache come	Yes	Migraine Criteria B
with sensitivity to light and sound?	No	
Q8. Yesterday, did you feel sick to the	Yes	Migraine Criteria B
stomach or throw-up with the headache?	No	
Q9. Yesterday, did you have your	Yes	
menstrual period (if female)?	No	
Q10. Yesterday, did you take any medicine for your headache?	Yes	Medication will only count as headache medication on a day a headache occurred.
, and the second	No	·
Q11. Yesterday, did you take any	Yes	
medication for pain other than headache?	No	
Q12. Yesterday, did you experience aura?	Yes	
	No	
Q13. Yesterday, did you experience any	Yes	
warning symptoms other than aura (prodrome symptoms) that a migraine was coming?	No No	

^a If "No" is answered for Q1, then the patients will skip Q2 - Q6, only answer questions Q7 - Q13.

Primary Measure: The Number of Monthly Migraine Headache Days

The primary measure is the number of monthly migraine headache days. A migraine headache day is defined as a calendar day on which a **migraine or probable migraine** occurs.

The primary measure of the number of monthly migraine headache days will be summarized from the daily ePRO data for each patient in that period (including 30 days of daily data from the baseline period prior to randomization, 6 months of daily data during the treatment phase, and 4 months of daily data during the post-treatment phase).

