The daily data will be aggregated, and the number of migraine headache days will be provided for each of the 30-day periods. In calculating the number of migraine headache days for each period, if the period is not equal to 30 days, the number of migraine headache days will be adjusted by multiplying the number of migraine headache days by (30/x) where 'x' is the total number of non-missing diary days in the period.

For the 4 months of the post-treatment period, the monthly interval will be derived as below. Firstly, the 2-month visit interval will be split into two one-month periods for efficacy measures. If the number of days between 2 visits (visit x+1 date - visit x date + 1) is even, the first half will be in the first one-month period and the second half will be in the second one-month period. If the number of days between 2 visits is odd, then the days will be split similarly, but the first one-month period will have 1 day more than the second one-month period. Secondly, after the two-month visit intervals are split into two one-month periods, the monthly data will be derived in the same way for each one-month period as for treatment phase. For patients who discontinued early during the post-treatment phase, if the date of discontinuation is within 30 days of previous visit date, all data between the previous visit date and the discontinuation date will go to 1 monthly period; if the date of discontinuation is more than 30 days of the previous visit date, then the first 30 days will be the first monthly period, and the rest will be considered as part of the second monthly period.

This approach to missing ePRO diary data assumes that the rate of migraine headaches per day is the same for days with missing and non-missing ePRO diary days, and it is missing at random. The same approach will also be applied to secondary and exploratory efficacy measures that are derived from ePRO data.

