Additionally, if the compliance rate for each monthly interval is \leq 50%, then all endpoints to be derived from the ePRO diary data for that one-month period will be considered missing. For the post-treatment phase, the derived one-month periods (resulting from splitting two-month visit interval) will be treated similarly. For a patient who discontinued early in the double-blind treatment phase or post-treatment phase, compliance rate for the last month of that study period will be calculated with the denominator of the maximum of 30 and the total number of calendar days in that month. For the rest of months and patients, the compliance rate will be calculated as described in Section 5.5.7.

Other Secondary and Exploratory Efficacy Measures

The same approach to adjusting the number of days within each period to a 30-day period and the same approach to imputing monthly data based on compliance as for the primary measure will be applied to all efficacy measures that are derived from ePRO diary data and need normalization to 30-day period, including:

- Number of ICHD migraine headache days is calculated as the number of calendar days in a 30-day period on which a migraine occurs. Probable migraine is excluded.
- **Number of headache days** is calculated as the number of calendar days in a 30-day period on which a headache occurs.
- Number of moderate to severe headache days is calculated as the number of calendar days in a 30-day period on which a headache occurs with a moderate or severe severity.
- **Number of headache hours** is calculated as the total number of headache hours in a 30-day period on which a headache occurred.
- **Number of migraine headache hours** is calculated as the total number of headache hours in a 30-day period on days when a migraine or probable migraine occurs.
- Number of migraine headache days with abortive (acute) medication use is calculated as the number of calendar days in a 30-day period on which migraine or probable migraine occurs and abortive (acute) medication is used.

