5.5.1.2. Handling of Dropouts or Missing Data

Two statistical approaches to handling missing data will be used as appropriate: repeated measures analyses and ANCOVA/ANOVA model using change from baseline to the average of observed monthly values during 6 months of treatment phase (for measures with objectives evaluated during the entire 6 months of treatment phase), or change from baseline to LOCF endpoint (for measures with objectives evaluated at Month 6).

For the repeated measures analyses, the model parameters are simultaneously estimated using restricted likelihood estimation incorporating all of the observed data. Estimates have been shown to be unbiased when the missing data are missing at random.

Please refer to Section 5.4.1 for approach to handling missing diary data for derivation of the number of migraine headache days and other efficacy measures (with the exception of migraine attacks) derived from ePRO data per 30-day period.

Approaches to Handling Missing Diary Data for the Derivation of Migraine Attack

For the analysis of migraine attack, the LOCF method will be used to impute the missing ePRO diary days. In other words, if the patient was migraine headache free on the day before the missing ePRO diary day, this would be carried forward as no migraine headache day until the actual next non-missing diary day. On the other hand, if the day before the missing diary day is a migraine headache day, then it would be carried forward as migraine headache day until the next non-missing diary day. The imputation will be carried out for all the missing diary days between the first non-missing to the last day during that period.

If the compliance rate for a monthly interval is $\leq 50\%$, the number of migraine attacks during that month will be considered missing. Please refer to Section 5.4.1 for compliance rate calculation.

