To assess the robustness of the MMRM results to deviations from normality assumption, a sensitivity analysis for the raw number of migraine headache days (the total number of migraine headache days for each interval without normalization to 30-day period) will be conducted with a repeated measures negative binomial regression analysis fitted with SAS PROC GLIMMIX. The model will include treatment, pooled region1, month, and treatment-by-month interaction, as well as the continuous fixed covariates of baseline number of monthly migraine headache days and baseline-by-month interaction, log (number of compliant calendar days within each month/30) as the offset in the model. In case of non-convergence, pooled region1 and/or baseline-by-month interaction may be excluded from the model. Directional consistency of treatment effects from this model and the primary analysis MMRM model as specified in Section 5.5.10.1 will be examined.

In addition, as another form of sensitivity analysis, residuals from the primary analysis MMRM model will be examined and outliers identified. Consistency of results before and after removing patients with outlier residuals will be examined.

Definition of Episodic Migraine Headache

This sensitivity analysis is to assess the robustness of the primary results to the deviation of minor change in the definition of migraine (See C. below). It is implemented by repeating the primary analysis using the number of monthly migraine headache days derived based on the

following definition of migraine, which aligns with migraine headache days definition in chronic migraine, but is considered relevant for the episodic population, as well.

A headache, with or without aura, of \geq 30 minutes duration with both of the following required features (A and B):

- A. At least 2 of the following headache characteristics:
 - Unilateral location
 - o Pulsatile quality
 - o Moderate or severe pain intensity
 - o Aggravation by or causing avoidance of routine physical activity

AND

- B. During headache at least one of the following:
 - o Nausea and/or vomiting
 - o Photophobia and phonophobia

OR

C. Patient takes a triptan or ergot derivative.

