Appendix Table 1. Description of Important Protocol Deviations

Category	Subcategory	Study-specific	Source	Methods of Identification
Informed Consent	Informed consent not obtained	Initial ICF date is missing or is after (Visit 1 Date or Visit 1 lab date)	Programmable – Stats	For all patients, if Initial ICF date is missing or after (Visit 1 date or Visit 1 lab date).
	Improper Consent	ICF not signed prior to initiation of protocol procedures	Non-Programmable- Monitor identified	Or determined by study team
Eligibility	Inclusion/ Exclusion	Age <18 or >65 years old at study entry	Non-Programmable- Monitor identified	
		BMI ≥40 at baseline	Programmable - Stats	
		Number of migraine headache days <4 or >14 at baseline	Programmable - Stats	Number of Normalized migraine headache days <4 or >14 at baseline
		Number of migraine attack <2 at baseline	Programmable - Stats	Number of Normalized migraine headache attack <2 at baseline
		Baseline ePRO compliance <80%	Programmable - Stats	
		Female patients who have a positive serum pregnancy test prior to randomization visit	Programmable – Stats	For randomized female patients, if serum pregnancy test is positive any time prior to Visit 3
		Female patients who have a positive or no serum pregnancy test prior to randomization visit	Non-Programmable- Monitor identified	

Category	Subcategory	Study-specific	Source	Methods of Identification
Eligibility	Eligibility Inclusion/ Exclusion	Insufficient Washout of prohibited migraine preventive medication for at least 30 days prior to Visit 2	Programmable - Stats	Patients must have discontinued such treatment at least 30 days prior to Visit 2.
		Insufficient Washout of Botulinum toxin A and B at least 4 months prior to Visit 2	Non-Programmable- Study Team identified	 Stats will create the list of patients meet this IPD criteria. Among those, the true IPDs will be manually added into non-programmable excel sheet.
		With suicidal ideation (Q4 or Q5) within past month of visit 1.	Programmable - Stats	Randomized patients with answer "yes" for C-SSRS suicidal ideation Q4 or Q5 occurred within past 1 month of Visit 1.
		Positive or No urine drug screen prior to randomization	Programmable - Stats	For randomized patients if prior to Visit 3, a patient has a positive UDS result and a repeated UDS not done or last repeat UDS is positive or UDS never collected.

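### SAP 5.4.1 applies the 30/x diary scaling only when a period is not 30 days long, which contradicts its own equal-rate assumption for missing diary days

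*SAP*

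**What the plan says.** Under Primary Measure, SAP 5.4.1 sums the daily diary entries within each period and states that "if the period is not equal to 30 days, the number of migraine headache days will be adjusted by multiplying the number of" those days by 30/x. It defines x as the total of non-missing diary days in the period. The section then explains that this way of treating missing diaries "assumes that the rate of migraine headaches per day is the same for days with missing and non-missing ePRO diary days".

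Other parts of the SAP bear on the rule:

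- **Baseline.** The data for the primary measure are described as "including 30 days of daily data from the baseline period prior to randomization".
- **Study Period IV.** For a patient who discontinues more than 30 days after the previous visit, "then the first 30 days will be the first monthly period".
- **Other diary measures.** "The same approach to adjusting the number of days within each period to a 30-day period" is carried over to the other diary endpoints that need normalising.
- **Section 5.5.1.2.** "Please refer to Section 5.4.1 for approach to handling missing diary data for derivation of the number of migraine headache days", with migraine attacks excepted; attacks have their own carry-forward rule for missing days.
- **Section 5.5.10.2.** The negative binomial sensitivity model uses unscaled counts with "log (number of compliant calendar days within each month/30) as the offset in the model". No condition on period length is attached.
- **Appendix Table 1.** The baseline eligibility deviation is identified as "Number of Normalized migraine headache days <4 or >14 at baseline".

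No passage says that the factor also applies to a period of exactly 30 days.

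**The concern.** The condition and the factor measure different things. The condition asks how long the period is; the factor corrects for how many diaries were completed. They agree when a 30-day period is complete, because 30/30 = 1. They part when a 30-day period has gaps: the text then applies no correction, and each missing day is in effect a day without migraine. The equal-rate assumption and the rule as written cannot both hold for such a period.

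The rule produces the primary endpoint and, by extension, the 50% and 75% responder endpoints and the acute-medication-day endpoint, which are key secondary. It also feeds the derived <8/≥8 baseline category. That category is a covariate (5.5.1.1), a log-rank stratum (5.5.10.3) and a subgroup (5.5.13), and Appendix Table 1 compares it with the category entered at randomisation. The 100% response endpoint is not affected, because zero stays zero under either reading. Two programmers working from the text could build different primary datasets.

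**Working it through.** The plan states no figure for this rule, so there is none to reproduce. The check is arithmetic on the rule itself.

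**Inputs from the documents.** Factor 30/x and its condition (SAP 5.4.1). Months with compliance of 50% or less are set to missing (SAP 5.4.1), so a retained 30-day month has x ≥ 16. Baseline diary completion is at least 80% (Protocol 5.1, criterion 5), so x ≥ 24 in a 30-day baseline. Visit targets and allowances come from the Schedule of Activities (Protocol Appendix 2). The diary-compliance day count is end date minus start date plus 1 (SAP 5.5.7). The 1.5-day treatment difference is the worked example in SAP 5.5.10.2. The patient counts below are illustrative assumptions.

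**Step 1: the two readings.** With y migraine days on x diaries, the literal value is y if the period is 30 days and y × 30/x otherwise; the scaled value is always y × 30/x.

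| Case | Literal | Always scaled |
|---|---|---|
| 6 on 24, 30-day period | 6.0 | 6 × 30/24 = 7.5 |
| 6 on 24, 29- or 31-day period | 7.5 | 7.5 |
| Baseline 7 on 24, 30 days | 7.0 (<8) | 8.75 (≥8) |
| Baseline 12 on 24, 30 days | 12.0 (within 4–14) | 15.0 (>14) |
| Acute-medication days, 5 on 24, 30 days | 5.0 | 6.25 |

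**Step 2: undercount in an affected period.** If C is the true 30-day count and m the missing fraction, the literal rule loses m × C.

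- m = 0.10: 0.10 × 4 = 0.4 to 0.10 × 8 = 0.8 days.
- m = 0.20: 0.20 × 4 = 0.8 to 0.20 × 8 = 1.6 days.
- Extreme of a retained month, x = 16: 1 − 16/30 = 46.7% of the count.

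**Step 3: responder status.** The direction depends on which period is left unscaled.

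- Complete baseline of 8, 30-day month with 4 on 24: literal reduction 1 − 4/8 = 50%; scaled 1 − 5/8 = 37.5%.
- Same baseline, 2 on 24: 75% literal; 1 − 2.5/8 = 68.75% scaled.
- 30-day baseline with 8 on 24, then a 31-day month with 4 on 25 (4 × 30/25 = 4.8): literal 1 − 4.8/8 = 40%; scaled 1 − 4.8/10 = 52%.

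**Step 4: where 30-day periods arise.** Baseline is described as 30 days of data. In Study Period IV, the early-discontinuation rule creates a 30-day first month. An on-target 60-day interval counts as 61 days and splits into 31 + 30. For treatment months the share is unknown. Assume each visit falls uniformly and independently in its window:

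| Months | Windows | End − start = 30 | With the +1 count |
|---|---|---|---|
| 1 | 14±1 plus 16±3 | 3/21 = 14.3% | 3/21 = 14.3% |
| 2–4 | 30±2 | 1/5 = 20% | 1/5 = 20% |
| 5–6 | 15±2 twice | 5/25 = 20% | 4/25 = 16% |
| Mean of six | | 19.0% | 17.7% |

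If every visit is exactly on target, the share is all months (end minus start) or none (with the +1).

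**Step 5: effect on the treatment difference.** With the same missing fraction in all arms, the difference shrinks by effect × share × m: from 1.5 × 0.177 × 0.10 = 0.027 to 1.5 × 0.190 × 0.20 = 0.057 days.

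**The case against.** The best reply is that the intent is plain. The section defines x as completed diaries, calls the rule its approach to missing diary data and states the equal-rate assumption. Section 5.5.1.2 refers back to it for that purpose, and Appendix Table 1 calls the baseline count normalised. A complete 30-day month has a factor of 1, so the condition may only describe when the factor makes a difference. The sensitivity model's offset fits the same intent; that model works on raw counts and needs its own adjustment.

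This stands as evidence of what was meant, and nothing shows that the data were derived wrongly. It does not repair the rule. Reading *period* as the number of completed diaries would remove the conflict, but the same sentence treats the diary days as lying within the period.

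Three further points limit the size of the problem:

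- The prospective baseline lasts 30 to 40 days. If that whole interval were the period, most baselines would be scaled even literally. The baseline examples rest on the SAP's description of 30 days of data and sit at the 80% completion limit.
- The 18–19% share is an assumption. Uniform timing over the 21- to 37-day dosing interval allowed in Appendix Table 1, which is equally an assumption, gives 1/17, about 6%, and an attenuation of about 0.01–0.02 days.
- The primary model uses the continuous baseline count, so the <8/≥8 category enters only other analyses. Both Study Period IV cases also lie outside the primary endpoint.

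**Conclusion.** The concern holds. As written, the rule gives values for incomplete 30-day periods that conflict with the SAP's own assumption, and nothing elsewhere overrides the condition. It should be fixed, as an error in a stated derivation of the primary endpoint.

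The consequence lies mainly at patient level. An unscaled baseline understates a reduction and an unscaled treatment month overstates it, so errors run both ways. The expected loss of treatment difference is a few hundredths of a day, assuming equal compliance across arms, 10–20% missing diaries and uniform visit timing. A larger bias between arms would need missingness that differs by arm. The documents give no basis for the direction or size of that.

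**What to change.** In SAP 5.4.1, replace the condition with a statement that the count is always multiplied by 30/x, where x is the number of non-missing diary days in the period. A complete 30-day month is unchanged, the equal-rate assumption is respected, and the derivation agrees with the offset in 5.5.10.2. Migraine attacks keep their separate rule for missing days in 5.5.1.2.

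The cost is one sentence and, if the literal rule was programmed, a one-line program change. No new data or patients are needed. Protocol 9.2 allows SAP changes only before unblinding, so the correction belongs before that point; afterwards it would be a choice made with results in view.
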